1. LIST OF ABBREVIATIONS

Table 1: List of Abbreviations

Abbreviation	Definition		
AE	Adverse event		
ALT	Alanine aminotransferase		
AST	Aspartate aminotransferase		
AUC	Area under the plasma concentration-time curve		
CGI-C	Clinical Global Impression of Change		
CGI-S	Clinical Global Impression of Severity		
C _{max}	Maximum plasma concentration		
СМН	Cochran-Mantel-Haenszel		
COVID	Coronavirus disease 2019		
CBI	Control-based Imputation		
CRF	Case report form		
CSR	Clinical Study Report		
C-SSRS	Columbia Suicide Severity Ration Scale		
C _{tau}	Concentration at trough		
DBP	Diastolic blood pressure		
DR	Delayed release		
ECG	Electrocardiogram		
eCRF	Electronic case report form		
ET	Essential tremor		
ETEA	Essential Tremor Embarrassment Assessment		
IB	Investigator's Brochure		
ICH	International Council for Harmonisation		
IEC	Independent Ethics Committee		
IR	Immediate release		
IRT	Interactive response technology		
ITT	Intent-to-treat		
MAR	Missing at Random		
MCMC	Markov chain Monte Carlo		
MDS	Movement Disorder Society		
MI	Multiple Imputation		
MMRM	Mixed-effect model with repeated measures		
MNAR	Missing not at Random		
PGI-C	Patient Global Impression of Change		
PGI-S	Patient Global Impression of Severity		

PI	Prescribing Information
PK	Pharmacokinetics
PMM	Predictive mean matching
QD	Once daily
QTcB	Bazett's Corrected QT interval
QTcF	Fridericia's corrected QT interval
QUEST	Quality of Life in Essential Tremor Questionnaire
SAE	Serious adverse event
SAP	Statistical analysis plan
SBP	Systolic blood pressure
SF-36v2	36-item Short Form Health Survey Version 2
SOC	System Organ Class
t _{1/2}	Terminal half-life
T-CALM	Phase 2 proof of concept study CX-8998-CLN02-001
TEAE	Treatment-emergent adverse event
TETRAS-ADL	The Essential Tremor Rating Assessment Scale – Activities of Daily Living
TETRAS-PS	The Essential Tremor Rating Assessment Scale – Performance Subscale
T_{max}	Time to maximum concentration
ULN	Upper limit of normal
WHO	World Health Organization
WOCBP	Women of childbearing potential

2. MODIFICATION HISTORY

Table 2 Version History for SAP

Version	Date	Description	
Version 1.0	31 May 2024	Final	

3. INTRODUCTION

The purpose of this SAP is to describe in detail the statistical methodology and planned analyses to be conducted for Protocol JZP385-201 for inclusion in the CSR. The current version is based on Protocol Amendment 04 dated 10 February 2023. Any additional analyses or deviation from the analyses outlined in this plan will be documented with rationale in the final CSR.

4. STUDY OBJECTIVES AND ENDPOINTS

4.1. Study Objectives

4.1.1. Primary Objective

The primary objective of the study is to evaluate the efficacy of JZP385 to improve functional and performance-based impairment due to tremor when administered once daily for up to 12 weeks at fixed doses of 10, 20, and 30 mg/day.

4.1.2. Key Secondary Objective

The key secondary objective of the study is to evaluate the efficacy of JZP385 to improve functional impairment due to tremor when administered once daily for up to 12 weeks at fixed doses of 10, 20, and 30 mg/day.

4.1.3. Secondary Objectives

The secondary objectives of the study are:

- To evaluate the efficacy of JZP385 to improve overall ET when administered once daily for up to 12 weeks at fixed doses of 10, 20, and 30 mg/day.
- To evaluate the safety and tolerability of JZP385 administered once daily for up to 12 weeks at fixed doses of 10, 20, and 30 mg/day in the treatment of adult participants with ET.

4.1.4. Exploratory Objectives

The exploratory objectives of the study are:

- To characterize the PK and exposure-response of JZP385 in adult participants with ET using sparse PK sampling.
- To evaluate the efficacy of JZP385 to improve overall ET when administered once daily for up to 12 weeks at fixed doses of 10, 20, and 30 mg/day.

4.2. Study Estimands and Endpoints

4.2.1. Primary Estimand

The primary estimand of the study is defined as:

- Treatment: 10, 20, and 30 mg/day JZP385 and placebo.
- Population: Adults with moderate to severe ET.
- Variable: Change from Baseline to Week 12 on the TETRAS composite outcome score*.
- Intercurrent events:
 - o Discontinuation of treatment due to an AE, for lack of efficacy, or any other reason. Participants who experience any intercurrent event will be included as if they did not experience the intercurrent event (hypothetical strategy).

- O Any change to concomitant anti-tremor medication use after the initiation of study intervention, including but not limited to the following: 1) starting a new antitremor medication, 2) stopping a concomitant antitremor medication, and 3) a dose or regimen change to current antitremor medication. This type of intercurrent event will be disregarded, and measurements obtained subsequently will be reported and analyzed (treatment policy).⁺
- Summary: Difference in the mean TETRAS composite outcome score from Baseline to Week 12 between each dose of JZP385 and placebo.
- * The TETRAS composite outcome score is the sum of modified items 1 to 11 of the TETRAS-ADL subscale and modified items 6 and 7 of the TETRAS-PS. For TETRAS-ADL, each item is modified from 5 response items to 4 response items by collapsing options 0 and 1 together and for TETRAS-PS, each item is modified from 9 response items (due to 0.5 scoring increments) to 4 response items. As such, the range of possible scores at each visit is 0 to 42.
- + A blinded review of all concomitant medications and therapies will be performed prior to database lock to determine the occurrence of this intercurrent event.

4.2.2. Key Secondary Estimand

The key secondary estimand is defined as:

- Treatment: 10, 20, and 30 mg/day JZP385 and placebo.
- Population: Adults with moderate to severe ET.
- Variable: Proportion of participants who improved (≥ 1 point decrease) from Baseline to Week 12 on the CGI-S*.
- Intercurrent events:
 - Discontinuation of treatment due to an AE, for lack of efficacy, or any other reason. Participants who experience any intercurrent event will be included as if they did not experience the intercurrent event (hypothetical strategy).
 - O Any change to concomitant antitremor medication use after the initiation of study intervention, including but not limited to the following: 1) starting a new antitremor medication, 2) stopping a concomitant antitremor medication, and 3) a dose or regimen change to current antitremor medication. This type of intercurrent event will be disregarded, and measurements obtained subsequently will be reported and analyzed (treatment policy).+
- Summary: Difference in the proportion of participants who improved (≥ 1 point decrease) from Baseline to Week 12 on the CGI-S between each dose of JZP385 and placebo.

^{*} The CGI-S is converted to a numerical scale of 1 to 5.

⁺ A blinded review of all concomitant medications and therapies will be performed prior to database lock to determine the occurrence of this intercurrent event.

4.2.3. Other Secondary Endpoints

- Secondary efficacy endpoints include the following:
 - o Proportion of participants reported as much improved on the CGI-C at Week 12.
 - o Proportion of participants reported as much improved on the PGI-C at Week 12.
 - Change from Baseline to Week 12 on the TETRAS-ADL subscale as summarized by each dose of JZP385and placebo.
 - Change from Baseline to Week 12 on the TETRAS-PS as summarized by each dose of JZP385 and placebo.
 - Change from Baseline to Week 12 on the upper limb score (item 4) of the TETRAS-PS as summarized by each dose of JZP385 and placebo.
 - Change from Baseline to Week 12 on the TETRAS total score, as summarized by each dose of JZP385 and placebo.
 - Change from Baseline to Week 12 on the QUEST as summarized by each dose of JZP385 and placebo.
 - Change from Baseline to Week 12 on the ETEA as summarized by each dose of JZP385 and placebo.
- Secondary safety and tolerability endpoint is:
 - o Incidence and severity of TEAEs, evaluation of safety laboratory assessments, vital signs, ECG results, C-SSRS results.

4.2.4. Exploratory Endpoints

- The exploratory PK endpoints include:
 - Plasma concentrations of JZP385 and its metabolites, if applicable, will be listed and summarized.
 - o PK parameters (e.g., Cmax, Tmax, t½, Ctau, AUC) of JZP385 and its metabolites, if applicable, will be estimated using population PK model and will be presented separately from the study data.
 - Population exposure-response analysis for JZP385 and its metabolites, if applicable, will be performed and will be presented separately from the study data.
- Exploratory efficacy endpoints include:
 - Change from Baseline to Week 12 on the sum of modified items 6 and 7 of the TETRAS-PS as summarized by each dose of JZP385 and placebo.
 - o Change from Baseline to Week 12 on the sum of modified items 1 to 11 of the TETRAS-ADL subscale as summarized by each dose of JZP385 and placebo.
 - o Proportion of participants who improved (≥ 1 point decrease) from Baseline to Weeks 4 and 8 on the CGI-S.

- Change from Baseline to Weeks 4 and 8 on the TETRAS composite outcome score, TETRAS-ADL, TETRAS-PS, TETRAS upper limb score (item 4), and TETRAS total score.
- o Proportion of participants reported as much improved on the PGI-C and CGI-C at Weeks 4 and 8.
- Change from Baseline to Week 12 on the 36-item Short Form Health Survey (SF-36) as summarized by each dose of JZP385 and placebo.
- Time course analysis on the sum of modified items 6 and 7 of the TETRAS-PS as summarized by each dose of JZP385 and placebo.

5. STUDY DESIGN

5.1. Summary of Study Design

This is a 12-week, double-blind, placebo-controlled, randomized, parallel-group, multicenter study of the safety and efficacy of JZP385 in the treatment of adult participants with moderate to severe ET.

[figure not shown]
The total duration of the study for each participant will be approximately 19 weeks. During the Screening Period, which will occur over a period of up to 35 days (an additional 28 days are permitted for participants who require washout of primidone), all participants will be evaluated for eligibility and will washout any prohibited medications. Participants eligible for the study will be randomized in a 1:1:1:1 ratio to receive once daily doses of 10, 20, or 30 mg JZP385 or placebo during a 12-week Double-blind Treatment Period. Randomization will be stratified by the TETRAS composite outcome score (≤ 17 or > 17) and the use of concomitant antitremor medication (Yes or No), as assessed at the Baseline Visit. JZP385 will be administered orally (PO) once daily in the morning on an empty stomach for 12 weeks. Dosing will be titrated as follows:

- Participants randomized to the 10 mg/day dose will initially receive 5 mg/day from Day 1 through Day 7, and 10 mg/day starting on Day 8.
- Participants randomized to the 20 mg/day dose will initially receive 5 mg/day from Day 1 through Day 7, 10 mg/day from Day 8 through Day 14, and 20 mg/day starting on Day 15.
- Participants randomized to the 30 mg/day dose will initially receive 5 mg/day from Day 1 through Day 7, 10 mg/day from Day 8 through Day 14, 20 mg/day from Day 15 through Day 21, and 30 mg/day starting on Day 22.

Once participants reach their assigned fixed dose, they will continue on that dose for the remainder of the planned 12-week treatment period. No dose adjustments will be allowed. Participants who cannot tolerate their assigned fixed dose of JZP385 will be withdrawn from the study.

The schema of study is shown in Figure 1.

Figure 1 Study Schema

5.2. Study Intervention

The study intervention planned for use in this study are described in table below.

Table 3 Study Intervention

Treatment Arm	Intervention Name ^a	Formulation	Unit Dose Strength(s) ^b	Dosage Level(s)	Route of Administration
1	Placebo	Capsule	Placebo 3 x placebo QD		Oral
2	JZP385 (DR2)	Capsule	Baseline Visit: 1 x 5 mg QD + 2 x 5 mg JZP385 placebo QD		Oral
			Weeks 2-12: 1 x 10 mg QD + 2 x 10 mg JZP385 placebo QD		
3	JZP385 (DR2)	Capsule	Baseline Visit: 1 x 5 mg QD + 2 x placebo QD 5 mg JZP385 placebo QD Week 2: 1 x 10 mg QD + 2 x placebo QD Weeks 3-12: 20 mg 2 x 10 mg QD + 1 x		Oral
4	JZP385 (DR2)	Capsule	JZP385 2 x 10 mg QD + 1 x JZP385 placebo QD Baseline Visit: 1 x 5 mg QD + 2 x 5 mg JZP385 placebo QD Week 2: 1 x 10 mg QD + 2 x 10 mg JZP385 placebo QD Week 3: 2 x 10 mg QD + 1 x 20 mg JZP385 placebo QD Weeks 4-12: 30 mg 3 x 10 mg QD JZP385 3 x 10 mg QD		Oral

Abbreviations: mg = milligram; QD = once daily; DR2 = delayed release formulation 2.

5.3. Power and Sample Size Calculations

A sample size of 80 evaluable participants per treatment group will provide 90% power to detect a difference of 3.1 points for the change from Baseline to Week 12 on the TETRAS composite outcome between JZP385 and placebo, with a common SD of 6.0 points. This sample size will also provide 91.7% power to detect a 26% between-treatment (assuming JZP385 at 66% versus placebo at 40%) difference in proportion of participants who improved by at least 1 point on the CGI-S from Baseline to Week 12. Assuming a 20% dropout rate, a total of 400 participants (100 participants per treatment group) will be randomized. The sample size calculation for the TETRAS composite outcome score is based on t-test and the CGI-S sample size calculation is based on chi-square test, both tests are 2-sided at the significance level of 0.05.

For the TETRAS composite outcome, at least 80% power is still achieved if there is a reduction of 0.4 points from the assumption in the difference in mean change from baseline (assuming a constant common standard deviation) or an increase in common standard deviation by 1 point, (assuming a constant difference in means). For the key secondary endpoint, at least 80% power is still achieved with comparable shifts in the assumptions.

The assumptions for these sample sizes were supported by the results from the Phase 2 study in Essential Tremor (Study CX-8998-CLN2-001 [T-CALM]), where the TETRAS ADL and PS were assessed. Using the same derived TETRAS composite outcome score, as defined in this SAP, and assessing the change from baseline to Day 28 in T-CALM, there was a difference in means between JZP385 and placebo of 3.04 and a difference in LS Means of 3.27. The standard deviation for the change from baseline was 5.86 in JZP385 and 5.47 in placebo. It is hypothesized that the treatment improvement will remain consistent over the longer study duration of JZP385-201, with a small increase in variability, thus supporting the above assumptions.

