9. STATISTICAL CONSIDERATIONS

9.1. Statistical Hypotheses

The null and alternative hypotheses for analysis of the primary estimand variable are:

 H_0 : $u_{JZP385} = u_{Placebo}$

 H_1 : $u_{JZP385} \neq u_{Placebo}$

Specifically, the null hypothesis states that there is no difference in the mean change on the TETRAS composite outcome score from Baseline to Week 12 between each dose of JZP385 and the placebo control group. The alternative hypothesis is that the mean change on the TETRAS composite outcome score from Baseline to Week 12 is not equal between each dose of JZP385 and the placebo control group.

The null and alternative hypotheses for analysis of the key secondary estimand variable are:

 H_0 : $p_{JZP385} = p_{Placebo}$

 H_1 : p JZP385 \neq p Placebo

Specifically, the null hypothesis states that there is no difference in the proportion of participants who improved by ≥ 1 point on the CGI-S from Baseline to Week 12 between each dose of JZP385 and the placebo control group. The alternative hypothesis is that the proportion of participants who improved by ≥ 1 point on the CGI-S from Baseline to Week 12 is not equal between each dose of JZP385 and the placebo control group.

Each JZP385 treatment group will be compared individually to placebo. The remaining secondary and exploratory endpoints will not be controlled within the formal hypothesis test for type I error. All safety analyses will be descriptive; no formal statistical testing will be performed.

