9.2. Sample Size Determination

A sample size of 80 evaluable participants per treatment group will provide 90% power to detect a difference of 3.1 points for the change from Baseline to Week 12 on the TETRAS composite outcome score between JZP385 and placebo, with a common SD of 6.0 points. This sample size will also provide 91.7% power to detect a 26% between-treatment (assuming JZP385 at 66% versus placebo at 40%) difference in proportion of participants who improved by at least 1 point on the CGI-S from Baseline to Week 12. Assuming a 20% dropout rate, a total of 400 participants (100 participants per treatment group) will be randomized. The sample size calculation for the TETRAS composite outcome score is based on t-test and the CGI-S sample size calculation is based on chi-square test, both tests are 2-sided at the significance level of 0.05.

For the TETRAS composite outcome score, at least 80% power is still achieved if there is a reduction of 0.4 points from the assumption in the difference in mean change from baseline (assuming a constant common standard deviation) or an increase in common standard deviation by 1 point, (assuming a constant difference in means).

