7.4. Level of Significance & Multiplicity Adjustment

To evaluate the efficacy of JZP385 at doses of 10, 20, and 30 mg/day compared with placebo, pairwise treatment difference between each of the 3 doses and placebo will be tested at the end of Week 12 for the primary and key secondary endpoints.

The family-wise Type I error rate will be controlled at a 2-sided significance level of 0.05. To address the multiplicity issue due to the multiple efficacy endpoints and doses, a fixed hierarchical testing sequence will be employed. The testing procedure will stop when a p-value exceeds 2-sided significance level of 0.05 (see below).

Statistical hypotheses to be tested (in sequential order):

- 1. Change in the TETRAS composite outcome score from Baseline to Week 12, 30 mg/day versus placebo.
- 2. Difference in proportion of participants who improved (≥ 1 point decrease) on the CGI-S from Baseline to Week 12, 30 mg/day versus placebo.
- 3. Change in the TETRAS composite outcome score from Baseline to Week 12, 20 mg/day versus placebo.
- 4. Difference in proportion of participants who improved (≥ 1 point decrease) on the CGI-S from Baseline to Week 12, 20 mg/day versus placebo.
- 5. Change in the TETRAS composite outcome score from Baseline to Week 12, 10 mg/day versus placebo.
- 6. Difference in proportion of participants who improved (≥ 1 point decrease) on the CGI-S from Baseline to Week 12, 10 mg/day versus placebo.

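### With the SD raised by 1 point, the named t-test gives 79.5% power for the TETRAS composite, not at least 80%; the 90% and 91.7% figures are correct per-comparison powers

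*SAP*

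**What the plan says.** Protocol 9.2 and SAP 5.3 give the same core calculation: "A sample size of 80 evaluable participants per treatment group will provide 90% power to detect a difference of 3.1 points" on the composite, with a common SD of 6.0. For the key secondary endpoint, "This sample size will also provide 91.7% power to detect a 26% between-treatment (assuming JZP385 at 66% versus placebo at 40%) difference". The composite figure is based on a t-test and the CGI-S figure on a chi-square test, and "both tests are 2-sided at the significance level of 0.05".

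Both sections then give two stress cases for the composite and say that power stays at 80% or more in each. In one, the difference is 0.4 points smaller with the SD unchanged. The other is "an increase in common standard deviation by 1 point, (assuming a constant difference in means").

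Protocol 9.1 adds: "Each JZP385 treatment group will be compared individually to placebo". SAP 7.4 and Protocol 9.4.1.1 set out a six-step fixed sequence, under which "The testing procedure will stop when a p-value exceeds 2-sided significance level of 0.05 (see below"). Step 1 is the 30 mg composite. Step 2 is the responder difference "on the CGI-S from Baseline to Week 12, 30 mg/day versus placebo".

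**The concern.** The SD statement is a numerical claim with every input given and the test named, so it can be checked directly. At 80 per arm it falls just below the floor that the documents state. A reader who relies on it would believe that the design keeps 80% power at an SD of 7.0, when it does so only up to about 6.96.

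A second matter is one of presentation. The power sections do not mention the fixed sequence. The 30 mg CGI-S is tested only after the 30 mg composite succeeds, so the chance of that confirmatory claim is a joint probability, which the single-test figure does not supply.

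**Working it through.** **Inputs** (SAP 5.3 and Protocol 9.2): n = 80 per arm; difference 3.1; SD 6.0; two-sided 0.05; t-test for the composite; chi-square test for CGI-S with 66% versus 40%. The stress cases are difference 3.1 − 0.4 = 2.7 with SD 6.0, and difference 3.1 with SD 6.0 + 1 = 7.0.

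**Formula for the composite.** The noncentrality is δ = difference / (SD × √(2/80)), with √(2/80) = 0.1581. Power comes from the noncentral t distribution with 2 × 80 − 2 = 158 degrees of freedom (critical value about 1.975). The normal approximation is Φ(δ − 1.960).

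| Case | δ | t-test | Normal approximation | Plan states |
|---|---|---|---|---|
| 3.1, SD 6.0 | 3.1/0.9487 = 3.268 | 90.1% | 90.5% | 90% |
| 2.7, SD 6.0 | 2.7/0.9487 = 2.846 | 80.8% | 81.2% | at least 80% |
| 3.1, SD 7.0 | 3.1/1.1068 = 2.801 | **79.5%** | 79.98% | at least 80% |

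The headline figure and the 0.4-point case reproduce. The SD case misses by 80.0 − 79.5 = 0.5 percentage points with the named test, and by 0.02 points with the normal approximation. With SD 7.0, the t-test gives 79.99% at 81 per arm and 80.5% at 82.

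**CGI-S.** The pooled proportion is (0.66 + 0.40)/2 = 0.53.

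- Null standard error: √(2 × 0.53 × 0.47/80) = 0.0789.
- Alternative standard error: √((0.66 × 0.34 + 0.40 × 0.60)/80) = 0.0762.
- Power: Φ((0.26 − 1.960 × 0.0789)/0.0762) = Φ(1.38), or 91.66% unrounded, which matches the stated 91.7%.
- Exact enumeration of the same uncorrected chi-square test over the two binomial distributions: 91.3%.

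**Dropout.** 80/(1 − 0.20) = 100 per arm and 400 in total, as stated.

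**Step 2 of the sequence.** The 30 mg CGI-S claim needs both 30 mg tests to succeed. For any dependence between the endpoints, the joint probability lies between p1 + p2 − 1 and min(p1, p2).

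- Lower limit with the exact CGI-S power: 0.901 + 0.913 − 1 = 0.814. With the formula power it would be 0.901 + 0.917 − 1 = 0.818.
- Upper limit: 0.901, the power of step 1.

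The range is therefore about 81% to 90%. No correlation has to be assumed, only that 30 mg has the planned effect on both endpoints.

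**The case against.** The strongest defence of the SD statement is that it is a rounding matter. The normal approximation gives 79.98%, which anyone would report as 80%, and two more participants per arm would restore the floor. That stands as to size. It does not make the sentence right: the documents name the t-test, and the wording is a floor that neither method reaches.

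On the sequence, a reader might infer that 91.7% is offered as the probability of the 30 mg CGI-S claim, and is therefore overstated. The documents do not support that reading. They tie the figure to one between-treatment difference, one named test and one significance level. Protocol 9.1 describes dose-by-dose comparisons with placebo, and the sequence is fully disclosed in SAP 7.4 and Protocol 9.4.1.1. Single-comparison power is a legitimate planning basis, and neither document undertakes to report joint power. That step 2 cannot be more likely than step 1 follows from the published order.

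A reader might also want numbers for the 20 mg and 10 mg steps, or conclude that those claims are underpowered. The documents give one planning effect for JZP385, do not say that it is expected at every dose, and give no correlation between the composite and CGI-S. Any such numbers would rest on the reviewer's own assumptions.

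**Conclusion.** The SD statement is wrong as written, by a small amount: 79.5% instead of at least 80% under the test that the documents name. The finding rests only on the documents' own inputs. It concerns a stress case, not the base case: SAP 5.3 cites SDs of 5.86 and 5.47 from the earlier phase 2 study, against 7.0 here.

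The 90%, 91.7% and 0.4-point figures are correct. The absence of sequential power is an omission that may usefully be filled, not an error. Step 2 power stays above 80% at its lowest under the planning assumptions.

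All figures are for the planning t-test and chi-square test. They do not describe the MMRM, or the CMH test with multiple imputation, that will be used for analysis. The point is minor, and nothing in it calls the design into question.

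**What to change.** 1. In SAP 5.3, separate the two stress cases. Keep at least 80% for the 0.4-point reduction (80.8%), and say that power is *approximately 80% (79.5%)* if the common SD rises by 1 point.
2. Make the same change in Protocol 9.2 at its next amendment. Under Protocol 10.1.1 amendments go to ethics and, as applicable, regulatory approval, so this wording does not justify an amendment of its own.
3. Optional: label 90% and 91.7% as *per-comparison power*, and add: *Under the fixed sequence, power for the 30 mg CGI-S claim cannot exceed that of the 30 mg composite (90%) and lies between about 81% and 90% under the planning assumptions, whatever the correlation between the endpoints.* Do not add figures for the 20 mg and 10 mg steps unless the sponsor states its own dose effects and correlation.

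The cost is a few words in each document. The optional sentence would put a less favourable figure beside 91.7%.
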